13.5.8.3 Vital Signs

Descriptive statistics (N, mean, SD, median, Q1, Q3, minimum, and maximum) will be used to summarize vital sign parameters (body temperature, systolic blood pressure, diastolic blood pressure, heart rate, and respiratory rate) at baseline, each post-baseline visit, and change from baseline to each post-baseline visit, by treatment group. Study baseline as defined in [Section 10.2](#) will be used.

Potentially clinically significant (PCS) post-baseline vital signs can be identified using the criteria shown in [Table 10](#) below. The number and percentage of subjects with any post-baseline treatment-emergent potentially clinically significant vital sign value will be tabulated by treatment group for each criterion. Any subject with a post-baseline result meeting the criteria, including those collected at unscheduled visits, will be counted.

Table 10 PCS Criteria for Vital Signs

| Parameter | Criteria |
|------------|---|
| Heart Rate | 
 • ≤ 50 bpm and decrease ≥ 15 bpm • ≥ 100 bpm and increase ≥ 15 bpm • ≥ 120 bpm and increase ≥ 15 bpm |
| SBP | 
 • ≤ 90 and decrease ≥ 20 mm Hg • < 140 mmHg and Increase ≥ 20 mmHg • ≥ 140 mmHg and Increase ≥ 20 mmHg • ≥ 160 mmHg and increase ≥ 20 mmHg |

| | |
|-----|--|
| DBP | 
 • < 100 mmHg and Increase \geq 20 mmHg • \geq 100 mmHg and Increase \geq 20 mmHg • \leq 50 mmHg and decrease \geq 15 mmHg • \geq 100 mmHg and increase \geq 15 mmHg |
|-----|--|

A plot will be presented to show the pattern of the SBP and DBP values over time by treatment group. Mean and SE will be presented in the plot. Additionally, spaghetti plots for SBP and DBP values over time will be provided for individual subjects with 1) maximum post-baseline SBP increased \geq 20 mmHg and SBP \geq 150 mmHg and 2) maximum post-baseline DBP increased \geq 20 mmHg and DBP \geq 100 mmHg. A shift plot displaying shifts from Baseline heart rate \leq 100 to maximum heart rate $>$ 100 post-Baseline will be provided for the safety analysis set. All vital signs will be presented in a data listing. All vital sign tables and listings will be reported on the Safety Analysis Set.

13.5.8.4 12-lead ECGs

The average of triplicates from 12-lead ECGs will be used to evaluate the change from baseline in ECG parameters (heart rate, PR interval, RR interval, QRS duration, QT interval, and QTcF interval). Descriptive statistics (N, mean, SD, median, Q1, Q3, minimum, and maximum) of ECG parameters will be presented for baseline, each post-baseline visit, and change from baseline to each post-baseline visit by treatment group. Study baseline defined in [Section 10.2](#) will be used. At Baseline, Week 1 and Week 4, descriptive statistics will also be presented for change from pre-dose to post-dose. All measurements, including those during unscheduled visits, will be provided in data listings.

The number and percentage of subjects whose QTcF values have met each of the criteria below, will be summarized by treatment group for baseline and post-baseline assessment. Unscheduled visit results, or any single result from the triplicates meeting criteria criterion will be included.

Table 11 PCS Criteria for ECG

| Parameter | Criteria |
|--------------------------------------|--|
| QTcF Interval | 
 • $>$ 450 msec for males • $>$ 470 msec for females • $>$ 500 msec for males and females |
| QTcF Interval Increase from Baseline | 
 • \geq 30 msec • \geq 60 msec |

All ECG tables and listings will be reported using the safety analysis set.

13.5.8.5 Physical Examinations

All physical examination findings will be listed in by-subject listings on the Safety Analysis Set. No tabulation summaries will be provided.

13.5.9 Pharmacokinetic Endpoints

Data from subjects who experience emesis within the PK sampling duration of IMR-687 on Study Day 1 or Week 4 visit, will be evaluated on a case-by-case basis for exclusion from concentration-time data and PK analysis descriptive summaries. The individual subject data will be listed.

If a quantifiable pre-dose concentration of IMR-687 is detected on Study Day 1 and this concentration is greater than 5% of the corresponding Cmax, all subject data will be excluded from all concentration-time and PK analysis descriptive summaries but will be included in the subject data listings.

Any protocol deviations or AEs which could impact PK parameter estimates will be evaluated in consultation with the Sponsor for exclusion from concentration-time data and PK analysis descriptive summaries. All data that are excluded in this manner will be listed and the reason for exclusion noted.

All plasma concentration-time data will be reported to the same number of significant figures as displayed in the bioanalytical data. λ_{daz} will be reported up to 4 decimal places and time-related parameters ($T_{1/2}$, T_{max} , and T_{last}) will be reported up to 3 decimal places. All other PK parameters will be reported to the same number of significant figures as displayed in the bioanalytical data.

The concentration-time data from subjects with sparse PK sampling collected using the sampling schedule reflected in protocol version 4.0 (08 Apr 2021) will be summarized descriptively and included in subject listings and analyzed for population PK. Noncompartmental analysis will not be performed with the PK data collected from these subjects. The concentration-time data from subjects with PK sampling collected using the sampling schedule reflected in the prior protocol versions (up to version 3.0; 29 Jan 2020) will be summarized descriptively and listed. The PK data from these latter subjects will be used for the estimation of PK parameters using noncompartmental analysis. All available PK data from this study will also be used to explore any relationship between IMR-687 exposure and clinical response, PD endpoints, or AEs, as data permit. These data will be analyzed together with PK data from other clinical studies for a population PK analysis, as appropriate. Population PK analysis and other exploratory PK/PD analyses are not within the scope of this SAP and will be detailed in a separate population PK analysis plan.

No analysis visit windows will be applied for reporting of plasma concentration-time data and PK analysis, nominal visit times will be used (i.e., Study Day 1 or Week 4).

13.5.9.1 Plasma Concentrations

Plasma concentrations of below the limit of quantification (BLQ) will be set to 0.01 ng/mL in the computation of mean concentration values. Descriptive statistics (number of subjects, mean, geometric mean, SD, coefficient of variation (%CV), geometric %CV, median, minimum, and maximum) will be used to summarize the plasma concentrations by dose and by study visit (i.e., Study Day 1 and Week 4 Visit) at each scheduled timepoint.

Linear and semi-logarithmic plots of the arithmetic mean (\pm SD) and geometric mean (\pm SD) plasma concentrations by scheduled sampling time will be provided by dose and by study visit. These plots will show time in hours. The plots will present all calculated means and will include a reference line for the lower limit of quantification (LLOQ).

Linear and semi-logarithmic plots of the individual plasma concentration by scheduled sampling time will be provided by subject (one subject per page) and by study visit. These plots will show time in hours. Individual plots will use the BLQ handling procedure described below for "Plasma Pharmacokinetic Parameters".

All individual subject plasma concentration data will be listed.

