5.2.2.3. Cardiovascular

In nonclinical safety pharmacology and 14-day GLP toxicology studies in beagle dogs, IMR-687 appeared to result in increases in heart rate that did not appear to be dose-dependent. In the safety pharmacology study in dogs, at doses of 75 mg/kg, statistically significant changes in heart rates were observed. In the 14-day toxicology study in dogs, the highest heart rates were noted at the highest dose level of 75 mg/kg but did not reach statistical significance. In a subsequent 9-month study in dogs at doses up to and including 50 mg/kg/day, there was no evidence of any increases in heart rate and there were no histopathological abnormalities noted in cardiac tissue. In healthy volunteers in the first-in-human study, at doses between 0.3 and 6 mg/kg, sporadic observations of sinus tachycardia (i.e., heart rates >100 bpm) occurred in various subjects, including a subject in the MAD on placebo. The contribution of concomitant AEs such as headache to the rise in heart rate could not be excluded. No dose dependency or dose-duration dependency was noted for these heart rate observations. No signs of prolongation of corrected QT interval, Fridericia's formula (QTcF) were noted in any cohort of healthy volunteers at any dose of IMR-687.

In the safety analysis of Study IMR-SCD-102, with respect to vital signs, there were no changes in systolic or diastolic blood pressure and pulse, and there were no changes in respiratory rate. In the IMR-SCD-102 clinical study, the mean interim steady-state AUC₀₋₂₄ was 16,300 ng•hr/mL for the 200 mg (~2.9 mg/kg) IMR-687 dose level. In the 39-week dog toxicology study mentioned above, mean AUC₀₋₂₄ was ≥87,500 ng•hr/mL at the NOAEL in female dogs, resulting in safety margins of at least ~5.3-fold for the 200 mg clinical dose. With dosing in the current study being up to 400 mg (≤6.7 mg/kg), safety margins of at least 2.7-fold are maintained.

Monitoring of vital signs is recommended for subjects in IMR-687 studies. In the event of noted persistent and/or clinically significant tachycardia, other causes of tachycardia, particularly pain and dehydration, should also be considered.

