10.0 Conventions and Derivations

10.1 Method for Handling Missing Data

There will be no imputation of incomplete or missing data unless specified otherwise in this SAP.

Please refer to [Appendix 4](#) for specific data handling rules, including missing last dose date for IA, incomplete/missing dates for adverse events and prior/concomitant medications, interpretation of non-numeric results (e.g. “< BLQ”, “>x.xx”) from PK and laboratory measures, etc.

Efficacy and PK imputation for missing data will be detailed in [Section 13.5](#).

Imputation will be noted in the footnotes. The original values/results will be presented in the data listings.

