13.5.9.2 Plasma Pharmacokinetic Parameters

Plasma PK parameters for IMR-687 will be estimated using noncompartmental methods with Phoenix® WinNonlin® Version 8.1 (Certara, USA). The PK parameters will be estimated from the concentration-time profiles, and AUCs will be calculated using a linear up/log down method using actual sampling times.

The apparent terminal elimination half-life, $T_{1/2}$, where determinable, will be calculated as the natural log of 2 divided by the terminal phase rate constant, λ_{daz} . The number of data points included in the regression will be determined by visual inspection, but a minimum of 3 data points in the terminal phase, excluding C_{max} , is required to estimate λ_{daz} . In order for λ_{daz} and λ_{az} derived parameters (AUC_{inf} , $T_{1/2}$, V_z/F , CL/F (single dose), and V_z/F to be reported, the adjusted r^2 value reported in Phoenix® WinNonlin® must be ≥ 0.80 .

For the purposes of estimating the PK parameters, BLQ values will be set to zero prior to the first measurable concentration and set to missing thereafter, including embedded BLQs. Scheduled sampling times will be used for the interim analyses and actual sampling times will be used for the final analysis.

Missing concentration-time data will be treated as missing except for the pre-dose plasma concentrations where a value of 0 will be imputed for Study Day 1 for the purposes of PK parameter estimation. Similarly for the Week 4 visit, missing concentration-time data will be treated as missing except for the pre-dose concentration following steady state dosing where the lowest concentration value over the dosing interval (C_{min}) will be used for imputation purposes. In addition, subjects must have a 24-hour PK sample collected at Study Day 1 and Week 4 in order to be included in the evaluation of accumulation ratio (RAUC). No extrapolation of AUC_{0-24} for any missing 24-hour PK sample will be performed.

For the final analysis, if the actual time is missing, the scheduled sampling time will be substituted and flagged. Subjects must have at least 4 consecutive non-zero post-dose plasma concentrations in order for their data to be considered evaluable. Profiles that do not meet this criterion will be flagged for exclusion.

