| 8. Multiple assessments for the same visit | Vital Sign, ECG and Laboratory assessments | 
 All ECG assessments are to be performed in triplicate. Valid assessments will be averaged to get the analysis value for that visit. |

| Category | Description | Data Handling Rule |
|---|--|---|
| | | 
 • Other than for ECG assessments, the last non-missing measurement taken prior to the date/time of first study drug (including unscheduled assessments) will be the analysis baseline. • Windowing will be applied for by-visit analyses. Unscheduled or Screening visits that occurred before the Baseline visit will not be assigned an analysis visit. The early discontinuation visit will be eligible for allocation to an analysis visit. • If one or more results for a variable are assigned to the same analysis visit, the result with the date closest to the protocol scheduled day will be used in the analysis. If 2 measurements in the same analysis visit window are equidistant from the protocol scheduled study day, the earliest measurement will be used in the analysis. • If multiple assessments are available on the same day (or for the same time point for ECG assessments), then the average of the assessments will be used in the analysis. • If both central and local assessments of the same lab test are available on the same day, the central result will take precedence over the local result. • All data will be listed in data listings. |
| 9. Special Lab Value Handling | Lab values with a prefix such as: '>', '<', '+' and 'Less than' Etc. | 
 • '>': use the available original value +0.001 in the analyses. • '<': use the available original value -0.001 in the analyses. • '+': use the available original value without the prefix in the analyses. • '≥': use the available original value in the analyses. • '≤': use the available original value in the analyses. |

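### Replacing BLQ plasma concentrations with a fixed 0.01 ng/mL makes the Day 1 and Week 4 geometric means and geometric CVs depend on that constant

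*SAP*

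**What the plan says.** SAP section 13.5.9.1 gives the rule for concentration summaries: "Plasma concentrations of below the limit of quantification (BLQ) will be set to 0.01 ng/mL in the computation of mean concentration values". The statistics that follow, by dose and scheduled timepoint, are "Descriptive statistics (number of subjects, mean, geometric mean, SD, coefficient of variation (%CV), geometric %CV, median, minimum, and maximum". The visits named are Study Day 1 and Week 4. Arithmetic and geometric mean plots are also planned, and they "will include a reference line for the lower limit of quantification (LLOQ"); the limit's value appears nowhere in either document. No count of BLQ samples is required, and no BLQ share is set above which geometric statistics are withheld.

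Two other BLQ provisions exist.

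- Section 13.5.9.2, for estimating PK parameters: "BLQ values will be set to zero prior to the first measurable concentration and set to missing thereafter, including embedded BLQs". Section 13.5.9.1 applies this rule to the individual plots as well.
- Section 10.1 names Appendix 4 as the place for "interpretation of non-numeric results (e.g. “< BLQ”, “>x.xx”) from PK and laboratory measures". The only matching entry there is item 9, headed for special laboratory values, which takes a result with a less-than prefix as the reported value minus 0.001.

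Section 13.5.9.2 also tabulates Ctrough for Day 1 and Week 4 together with Weeks 24 and 52, and Table 12 lists Ctrough as a PK parameter. The SAP does not say which BLQ rule applies to those tables.

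**The concern.** A geometric mean averages logarithms, so a value far below the rest carries great weight, and the geometric CV is more sensitive still. The constant 0.01 ng/mL is several orders of magnitude below the drug's concentrations: Protocol section 5.2.2.3 reports a mean interim steady-state AUC over 24 hours that "was 16,300 ng•hr/mL for the 200 mg (~2.9 mg/kg) IMR-687 dose level", an average of about 679 ng/mL.

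BLQ samples are plausible in this design. SAP Appendix 3 places the current post-dose samples at 15 minutes, 30 minutes and 3 hours. Subjects are directed to dose with food, and Protocol section 4.2.3.1 says food delays the median time to peak by about 3 hours. Two of the three post-dose samples are therefore drawn early in absorption. Under SAP section 13.5.9, subjects on this schedule get no noncompartmental analysis, so descriptive concentration summaries matter more for them. If the rule is followed as written, the early rows of those tables could reflect the constant rather than the drug.

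**Working it through.** The plan gives no figure to reproduce; the check is the direct effect of the substitution.

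**Inputs from the documents.** Substituted value c = 0.01 ng/mL (SAP 13.5.9.1). Exposure scale at 200 mg: 16,300 / 24 = 679 ng/mL on average (Protocol 5.2.2.3).

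**Assumptions.** G is the geometric mean of the quantifiable samples: 500, 50 or 10 ng/mL. The first is near the 24-hour average; the lower two suit early fed samples better. The quantifiable log SD is 0.5, a geometric CV of sqrt(exp(0.25) − 1) = 53%. The BLQ share is p. The LLOQ, where needed, is 1 to 10 ng/mL.

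**Geometric mean.** Reported / G = (c/G)^p.

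- G = 500: (0.01/500)^0.05 = 0.58; with p = 0.10, 0.34.
- G = 50: (0.01/50)^0.05 = 0.65.
- G = 10: (0.01/10)^0.05 = 0.71.

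**Geometric CV.** Log variance V = (1 − p) × 0.25 + p(1 − p) × [ln(G/c)]²; geometric CV = sqrt(exp(V) − 1).

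- G = 500, p = 0.05: V = 0.2375 + 0.0475 × 10.82² = 5.80, giving about 1,800%.
- G = 500, p = 0.10: V = 0.225 + 0.09 × 10.82² = 10.76, giving about 22,000%.
- G = 10, p = 0.05: V = 0.2375 + 0.0475 × 6.91² = 2.50, giving about 335%.

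**Arithmetic mean and median.** With 35 samples, 3 of them BLQ, G = 679 and a quantifiable geometric CV of 50%, the geometric mean is 679 × (0.01/679)^(3/35) = 262 ng/mL. The arithmetic mean moves only from 756 to 691 and the median from 679 to 642.

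**All samples BLQ.** If every Day 1 pre-dose sample is BLQ, that row shows a geometric mean of 0.01 and a geometric CV of 0%, both produced by the constant.

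**Against an LLOQ/2 rule.** The ratio of the two reported geometric means is (0.01/(LLOQ/2))^p, which does not depend on G. At p = 0.05 it is (0.01/0.5)^0.05 = 0.82 for an LLOQ of 1 and (0.01/5)^0.05 = 0.73 for an LLOQ of 10. The fixed constant therefore gives a value 18% to 27% lower.

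**Does LLOQ/2 cure the CV?** At G = 500 and p = 0.05, V = 0.2375 + 0.0475 × [ln(1,000)]² = 2.50 for an LLOQ of 1 and 0.2375 + 0.0475 × [ln(100)]² = 1.25 for an LLOQ of 10. The geometric CVs are about 335% and 157%, against 53% without BLQ samples, so it does not.

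**The case against.** Several points on the other side stand.

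- The quantifiable-only geometric mean is a generous benchmark. It omits the low samples, so some reduction is correct. Against LLOQ/2 the geometric-mean shortfall at 5% BLQ is 18% to 27%, and that depends on an LLOQ the documents do not give.
- A value near 500 ng/mL does not fit early samples after food. At 10 to 50 ng/mL the ratio is milder, 0.65 to 0.71.
- The same tables carry the median, minimum and arithmetic mean, and the listings show every value. A careful reader would notice a distorted geometric mean.

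Stronger readings are tempting but unsupported.

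- *The rule distorts the Week 24 and 52 troughs and undermines the IC90 coverage rationale.* Section 13.5.9.1 names only Day 1 and Week 4; the later troughs fall under 13.5.9.2, where the governing rule is unclear. The coverage statement in Protocol section 5.1 is a dose-selection prediction that these tables do not test.
- *These tables are the only PK output for Version 4.0 subjects.* Section 13.5.9 also plans population PK and exposure-response work, the population PK under a separate plan.
- *The SAP gives one sample two binding values.* Appendix 4 item 9 is headed for laboratory values, and 13.5.9.1 is the more specific rule for plasma concentrations. The section 10.1 pointer is loose wording that needs correcting, not a firm contradiction.
- *The dose groups would appear in reverse order.* That needs particular BLQ counts in each arm, and the documents give none.

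None of this supplies a reason for 0.01 ng/mL or makes the geometric CV usable when BLQ samples occur.

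**Conclusion.** The point holds for the geometric means, geometric CVs and geometric-mean plots on Study Day 1 and Week 4. Section 13.5.9.1 speaks of mean concentration values; applying it to the geometric CV is the natural reading. With 5% BLQ, the geometric mean falls to about 0.58 to 0.71 of the quantifiable value for assumed concentrations of 500 down to 10 ng/mL, and at 500 ng/mL with log SD 0.5 the geometric CV is about 1,800%. BLQ frequency, LLOQ and early concentration levels are all assumptions. One can say only that the SAP states no link between 0.01 and the LLOQ, not that none exists. The harm is confined to descriptive PK tables and mean plots: arithmetic means and medians barely change, and no hypothesis test, alpha, power figure or noncompartmental parameter uses the constant. It is worth correcting because the correction is cheap.

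**What to change.** In SAP section 13.5.9.1:

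1. Replace 0.01 ng/mL with a rule tied to the stated LLOQ, for example BLQ = 0 for arithmetic means and LLOQ/2 for geometric statistics.
2. Show n (%) BLQ at every timepoint.
3. Where the BLQ share exceeds a low prespecified limit, report the median and quartiles instead of the geometric mean and geometric CV. A limit as high as one third would be too lax. With LLOQ/2, 30% BLQ, G = 500 and an LLOQ of 1 to 10, the geometric mean is (0.5/500)^0.3 = 0.13 to (5/500)^0.3 = 0.25 of G. There V = 0.7 × 0.25 + 0.21 × [ln(G/(LLOQ/2))]² runs from 10.2 down to 4.6, a geometric CV of about 16,000% down to 1,000%.

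Elsewhere in the SAP:

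4. Correct section 10.1 so that Appendix 4 item 9 does not apply to PK concentrations.
5. State in section 13.5.9.2 which BLQ rule governs the Ctrough tables.

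The cost is a few sentences and a small programming change. The downside is that some geometric statistics will not be shown at early timepoints.

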13.5.9.2 Plasma Pharmacokinetic Parameters

Plasma PK parameters for IMR-687 will be estimated using noncompartmental methods with Phoenix® WinNonlin® Version 8.1 (Certara, USA). The PK parameters will be estimated from the concentration-time profiles, and AUCs will be calculated using a linear up/log down method using actual sampling times.

The apparent terminal elimination half-life, $T_{1/2}$, where determinable, will be calculated as the natural log of 2 divided by the terminal phase rate constant, λ_{daz} . The number of data points included in the regression will be determined by visual inspection, but a minimum of 3 data points in the terminal phase, excluding C_{max} , is required to estimate λ_{daz} . In order for λ_{daz} and λ_{az} derived parameters (AUC_{inf} , $T_{1/2}$, V_z/F , CL/F (single dose), and V_z/F to be reported, the adjusted r^2 value reported in Phoenix® WinNonlin® must be ≥ 0.80 .

For the purposes of estimating the PK parameters, BLQ values will be set to zero prior to the first measurable concentration and set to missing thereafter, including embedded BLQs. Scheduled sampling times will be used for the interim analyses and actual sampling times will be used for the final analysis.

Missing concentration-time data will be treated as missing except for the pre-dose plasma concentrations where a value of 0 will be imputed for Study Day 1 for the purposes of PK parameter estimation. Similarly for the Week 4 visit, missing concentration-time data will be treated as missing except for the pre-dose concentration following steady state dosing where the lowest concentration value over the dosing interval (C_{min}) will be used for imputation purposes. In addition, subjects must have a 24-hour PK sample collected at Study Day 1 and Week 4 in order to be included in the evaluation of accumulation ratio (RAUC). No extrapolation of AUC_{0-24} for any missing 24-hour PK sample will be performed.

For the final analysis, if the actual time is missing, the scheduled sampling time will be substituted and flagged. Subjects must have at least 4 consecutive non-zero post-dose plasma concentrations in order for their data to be considered evaluable. Profiles that do not meet this criterion will be flagged for exclusion.

Descriptive statistics (number of subjects, mean, geometric mean, SD, %CV, geometric %CV, median, minimum, and maximum) will be used to summarize the PK parameters by dose, timepoint, and by study visit. Additional PK evaluations may be performed as needed.

C_{trough} concentrations for Study Day 1 and Week 4 will be summarized in tables along with C_{trough} concentrations at Week 24 and Week 52.

All individual subject PK parameters will be listed by subject ID and treatment group.

The following PK parameters for IMR-687 may be computed, where feasible. Additional PK parameters may be determined:

Table 12 PK Parameters for IMR-687

| Parameter | Description |
|----------------------------------|--|
| Study Day 1 (Single Dose) | |
| C_{max} | Maximum plasma concentration post-dose. Observed peak analyte concentration obtained directly from the experimental data without interpolation, expressed in concentration units. |
| T_{max} | Time to maximum plasma concentration post-dose. First observed time to reach peak analyte concentration obtained directly from the experimental data without interpolation, expressed in time units. |
| T_{last} | Time of last measurable plasma concentration. |
| C_{trough} | Concentration at the end of the dosing interval. |
| AUC_{last} | Area under the concentration-time curve from time 0 to the last measurable concentration post-dose. |
| AUC_{inf} | Area under the concentration-time curve from time 0 to infinity, calculated as $AUC_{last} + (C_{last}/\Lambda_{z})$. |
| Λ_{z} | Apparent terminal elimination phase rate constant. |
| $T_{1/2}$ | Apparent terminal elimination half-life. |
| CL/F | Apparent total body clearance from oral administration, calculated as Dose/ AUC_{inf} . |
| V_z/F | Apparent volume of distribution from oral administration, calculated as Dose/ $\Lambda_{z} \times AUC_{inf}$. |
| Week 4 (Steady State) | |
| $C_{max,ss}$ | Maximum plasma concentration post-dose at steady state. Observed peak analyte concentration obtained directly from the experimental data without interpolation, expressed in concentration units. |

| Parameter | Description |
|---------------------|--|
| T _{max,ss} | Time to maximum plasma concentration post-dose at steady state. First observed time to reach peak analyte concentration obtained directly from the experimental data without interpolation, expressed in time units. |
| T _{last} | Time of last measurable plasma concentration. |
| C _{trough} | Concentration at the end of the dosing interval. |
| AUC ₀₋₂₄ | Area under the concentration-time curve from time 0 to 24 hours post-dose. |
| Lambda _z | Apparent terminal elimination phase rate constant. |
| CL _{ss} /F | Apparent total body clearance from oral administration at steady state, calculated as Dose/AUC ₀₋₂₄ . |
| V _z /F | Apparent volume of distribution from oral administration at steady state, calculated as Dose/lambda _z × AUC ₀₋₂₄ |
| RAUC | Accumulation ratio, calculated as AUC ₀₋₂₄ (Week 4)/ AUC _{last} (Study Day 1; AUC _{last} t = 24 hours). |

C_{last} = last observed measurable plasma concentration

